The aim of this study is to compare ridge dimensional changes between densification and standard drilling protocols. Additionally, primary and secondary stability of implants placed by bone densification and standard drilling protocols will be compared. A comparison of the insertion torque values (measured in Ncm) and temporal (immediate, 3, 6, and 12 weeks) implant stability quotients at osteotomies prepared with standard drilling procedures or when subjected to osseodensification surgical instrumentation will be performed. Dimensional changes will be measured before and after completion of the implant osteotomy, and compared between standard and osseodensification surgical instrumentation. Finally, volumetric changes and ridge dimensional changes will be evaluated between initial CBCT and 6 months follow-up CBCT.

Study Design

Twenty patients (we will try to balance male and female population sample if it is possible) in need to receive at least 2 dental implants in single-unit or larger span edentulous spaces will be selected. Nonsmoking and not systemically compromised patients will be selected. The following scenarios will be chosen to rehabilitate the anterior and posterior regions in this study.

- **If maxilla:**
 - split-mouth, implant insertion to replace anterior or posterior teeth: one side will receive osseodensification drilling instrumentation and the other standard drilling. Site selection is randomized by coin toss.
 - same side, adjacent teeth: Site selection will be randomized by coin toss.
- **If mandible:**
 - split-mouth or same side surgical instrumentations will be performed, as described for maxilla.

Surgical technique

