- Patient with malignant tumor.
- Patients on daily dose of steroids.
- Patients with history of chemotherapy or radiation for the last 12 months.

Study Procedures

Forty implants will be paired and placed in 20 patients using OsseoDensification (OD) protocol as test, and using standard drilling (SD) protocol as control. Sites will be randomly assigned in comparative patients prior to flap reflection.

Primary Outcome Measures:

All ridge dimensions will be measured immediately after flap reflection and after final osteotomy preparation: at crest, 5 mm and 10 mm apical from the crest. A surgical guide will be fabricated for the implant surgery which will also be marked on the buccal indicating the middle of the osteotomy and the ridge dimensions will be measured using the mark as a standard reference. The measurements will be completed the day of surgery only.

Secondary Outcome Measures:

1. All implants' primary stability will be measured by insertion torque values and by resonance frequency analysis (ISQ) immediately after implant placement (T0). Resonance frequency analysis will be measured at three weeks (T1), six weeks (T2), and twelve weeks (T3) post implant placement.
2. At 6 months all patients will receive CBCT for volumetric analysis.

Digital radiographs (periapical radiographs PA) will be taken prior to implant placement, post placement, and at 6 weeks. Cone beam computer tomography (CBCT) will be obtained prior to implant placement for implant planning and fabrication of a surgical guide, and at 6 months post-implantation for volumetric analysis.

In any incidence of less than 1 mm buccal plate thickness has resulted after bone preparation, bone grafting will be done post implant placement and complete implant coverage will be achieved for two-stage healing protocol. Cases requiring bone grafting will be excluded from the CBCT analysis at 6 months and from 3-week (T1) and 6-week (T2) ISQ readings. Cases requiring two-stage healing will also be excluded from 3-week (T1) and 6-week (T2) ISQ readings, but will be included in 12-week (T3) ISQ readings at second stage surgery.

At 12 weeks all patients will receive dental restorations. Implants' restorative phase will be initiated at any time resonance frequency analysis become equal or more than ISQ 68.

Why 3 weeks, 6 weeks, and 12 weeks ISQ measurements:

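### Sites are assigned before flap reflection and the baseline ridge width is read after it with no masking described, so the baseline half of the primary change score may be read with allocation known; separately, two calipers are named and only one is calibrated

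*Combined protocol and SAP*

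**What the plan says.** All references are to the combined protocol and SAP.

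- **Assignment.** Study Design gives the method: "Site selection is randomized by coin toss". The same method covers adjacent sites, and the mandible follows the maxilla. Study Procedures gives the timing: "Sites will be randomly assigned in comparative patients prior to flap reflection".
- **Primary outcome.** Under Primary Outcome Measures, "All ridge dimensions will be measured immediately after flap reflection and after final osteotomy preparation", at the crest and at 5 mm and 10 mm below it. Also, "The measurements will be completed the day of surgery only". A mark on the surgical guide fixes the position: "the ridge dimensions will be measured using the mark as a standard reference".
- **Pairs.** "Forty implants will be paired and placed in 20 patients". Study Design admits patients "in need to receive at least 2 dental implants in single-unit or larger span edentulous spaces will be selected", so a patient may have more than two candidate sites. The plan does not say how or when the study pair is chosen.
- **Masking.** No visible text says who tosses the coin, who reads the caliper, or whether the reader is kept unaware of the result. One item under Quality control and assurance is not shown and could not be checked.
- **Calipers.** Surgical technique names a Krekler gauge for ridge change at implantation, and the product list includes one Krekler and no Mitutoyo. Quality control and assurance names a Mitutoyo digital caliper for ridge dimensions, states its accuracy, and limits caliper calibration to it. Primary Outcome Measures names neither.

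**The concern.** The primary outcome is a manual change score: width after the osteotomy minus width before it, compared between two sites in the same patient. The first reading carries as much weight as the second. If the reader knows which site will be densified, a baseline read slightly low there, or slightly high at the standard-drilling site, appears in the result as expansion. Pairing does not remove such an error, because it differs between the two members of the pair. The caliper reading of the undrilled ridge cannot be repeated once the site is drilled.

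Masking the reading after drilling is hardly feasible. The baseline is the one primary reading that could be masked cheaply, and the stated order gives that up.

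The caliper discrepancy is a different and smaller matter. It leaves unclear which instrument produces the primary data and whether its readers are calibrated on it.

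**Working it through.** **Order of events.** Putting Study Procedures and Primary Outcome Measures together gives: assign, raise the flap, read the baseline, prepare the osteotomy, read again. The two sections agree. The gap is that nothing visible keeps the assignment from the reader at the third step. The guide mark controls where the width is read, not what the reader knows.

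**How much an error could matter.** The plan gives no power, effect size, paired SD or reading error, so there is no figure of its own to reproduce. The following is a sensitivity calculation.

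Inputs:
- n = 20 pairs (Study Procedures), paired t-test (Statistics section), 19 degrees of freedom.
- Two-sided 5% level: assumed.
- SD of the paired difference, s: assumed 0.66 to 1.5 mm. The value 0.66 is the only spread quoted for ridge change (Background Information); it describes single sites in 1 to 3 mm ridges and is not a paired SD. The middle value is 0.66 × √2 = 0.933. The value 1.5 is an assumed upper figure.
- Systematic between-arm reading error, b: assumed 0.25 or 0.10 mm, in the same direction in every patient.
- Share of b that arises at baseline: assumed one half.

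Formula: with no true difference, the t statistic follows a noncentral t distribution with noncentrality b√n/s. For example, 0.25 × √20 / 0.66 = 1.694. The false-positive rate is the probability that |t| exceeds 2.093. With b = 0 it is 5.0%.

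Remaining error if baseline is read before the reveal:
- in all pairs: 0.25 − 0.125 = 0.125 mm;
- in half the pairs: (0.25 + 0.125)/2 = 0.1875 mm on average. The unequal error adds little spread: √(0.66² + 0.0625²) = 0.663.

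The corresponding values for 0.10 mm are 0.05 and 0.075 mm.

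| Case | b (mm) | s = 0.66 | s = 0.933 | s = 1.5 |
|---|---|---|---|---|
| Assumed error 0.25, no change to plan | 0.25 | 36.3% | 20.6% | 10.9% |
| Baseline first in half the pairs | 0.1875 | 22.6% | 13.7% | 8.3% |
| Baseline first in all pairs | 0.125 | 12.7% | 8.8% | 6.4% |
| Assumed error 0.10, no change to plan | 0.10 | 9.9% | 7.4% | 5.9% |
| Baseline first in half the pairs | 0.075 | 7.7% | 6.3% | 5.5% |
| Baseline first in all pairs | 0.05 | 6.2% | 5.6% | 5.2% |

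**Calipers.** If one instrument with a constant offset c is used throughout, the change at a site is (after + c) − (before + c) = after − before. The offset cancels. Harm needs mixed instruments, or readings of differing precision.

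**The case against.** Several points on the other side are sound.

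- **No contradiction and no demonstrated bias.** Assigning before the flap is not an error in itself, and it has a benefit: the allocation is fixed before anyone sees the exposed ridges. A reader might infer that the caliper reader knows the allocation, or that the primary result will be biased. The documents say neither; they are silent on who reads.
- **The coin toss is not defective.** A reader might infer that it must be replaced by a concealed list. Every patient receives both techniques, so the toss cannot steer enrolment to an arm, and a fair toss cannot be foreseen. What matters is when the result becomes known. A list with opaque envelopes adds an audit trail and cures no identified fault.
- **The gain is conditional.** The plan allows split-mouth cases and does not say that both sites are open before either is drilled. The number of pairs in which the baseline can come first is unknown, so the fall to 13% to 6% cannot be promised.
- **A second record of baseline width exists.** All patients have a pre-operative CBCT. It is not planned as a check on the caliper: its plane is defined by the placed implant and it is compared with the later scan. Also, "Cases requiring bone grafting will be excluded from the CBCT analysis at 6 months". It would be a useful cross-check, with gaps.

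What survives is narrower. The plan fixes an order that lets the baseline be read with the allocation known, and for some or all pairs a better order is available at almost no cost.

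**Conclusion.** The point holds as a cheap improvement to how the primary outcome is measured, not as a finding of bias. Its size cannot be established from the documents. Error size, direction, paired SD and baseline share are all assumed. At 0.25 mm the false-positive rate would be 36% to 11%; at 0.10 mm it would be 10% to 6%, which is small. Reading the baseline first removes only the baseline part, and only in pairs where that is possible. The reading after the osteotomy enters the score equally and stays unmasked.

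The two caliper names are a real inconsistency. A reader might infer that they bias the primary outcome. If one caliper is used throughout, a constant offset cancels, so the matter is one of precision and reporting.

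**What to change.** 1. Before surgery, record from the implant plan which two sites form the study pair, and label them site 1 and site 2.
2. Where both sites will in any case be open before either is drilled, record baseline widths at both sites and all three levels first. Only then toss the coin (heads: site 1 receives osseodensification) or reveal the allocation, and write the result down at once.
3. Otherwise keep assignment before the flap, leave the surgical sequence as it is, and record whether the baseline reader knew the allocation.
4. Edit the coin-toss sentences in Study Design and the assignment sentence in Study Procedures together, so that they agree. State who takes each reading, and report the post-osteotomy reading as unmasked.
5. Reconcile Surgical technique, Quality control and assurance and the product list to one caliper. Use it for every primary reading and calibrate on it.

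A list prepared in advance with opaque envelopes is optional.

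Cost: a line in each patient's planning record, a few edited sentences, and a short pause before the reveal in step 2. There are no extra visits. Some baselines under step 3 may stay unmasked, so bias is reduced and not removed.

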Studies conducted comparing standard drilling (SD) with osseodensification drilling (OD) show significant increase in implant primary and secondary stability with OD. Through surgical compaction of bone into marrow space, OD has been found to increase the insertion torque values regardless of the type of implant surface (machined versus acid-etched implant surfaces).¹ In another study, significantly lower insertion torques have been noted when SD was utilized.² Additionally, through histomorphometric analysis, greater bone-to-implant contact (BIC) and bone area fraction occupancy (BAFO) has been demonstrated with OD.² Autologous bone chips have been recorded with greater frequency in the OD group compared to the SD group.³ The autologous bone chips acted as nucleating surfaces promoting new bone formation resulting in greater implant stability and bone density.³ Another study verified the infrequent presence of bone chips in the SD group compared to the commonly observed presence of bone chips in the OD groups.⁴ When clockwise (CW) and counterclockwise (CCW) OD was compared, higher volume of bone chips was observed in the CCW OD group. Further research has demonstrated increase in ridge dimensions with the OD method. Specifically, narrower ridges measuring 1-3 mm at the crest demonstrated the greatest increase in width accounting for 2.83 ± 0.66 mm increase. Greater changes in ridge width were noted at the crest versus 10 mm from the crest.⁵

Hypothesis:

- Bone Densification protocol does not increase implant primary and secondary stability values in 0-6 wks as compared to standard drilling protocol.
- Bone Densification does not increase ridge dimensions as compared to standard drilling protocol.
- Bone densification does not increase bone volume and density as compared to standard drilling protocol.
- There is no significant difference between bone densification and standard drilling protocols.

Objectives

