Final implant (NobelReplace® Conical) and respective bur diameter for either osseodensification instrumentation and conventional drilling will be either 3.5 mm, 4.3 mm or 5.0 mm. Implant lengths will be from 8.0 up to 13.0 mm. Versah (Fig. 2) and NobelReplace ® Conical implant surgical kit (Fig. 1) present burs with identical diameter and instrumentation will be performed so last bur diameter matches with chosen implant diameter. When using Versah, counterclockwise drilling will be performed in maxilla, and in mandible clockwise drilling. Before surgery, all patients will receive intraoral scans and will be subjected to tomographic examination of the edentulous site for virtual implant planning, surgical planning, implant selection, and fabrication of a surgical guide with a mark on the buccal aspect identifying the middle of the osteotomy. The osseodensification technique will be used for comparison with conventional drilling regarding ridge dimensional changes measured with a ridge caliber (Krekler Sliding Caliper Round Gauge Dental Instrument) at

implantation (T0); and insertion torque (IT) values and implant stability quotients (ISQ) at implantation (T0), 3 (T1,) 6 (T2), and at 12 weeks (T3). ISQ will be measured with Osstell ISQ meter. Data will be evaluated with paired t-tests. After T0, patients will receive a healing abutment which will be removed and repositioned for T1, T2, and T3 evaluations. After 12 weeks patients will be prosthetically restored if insertion torque was 35 Ncm and/or ISQ values are 68. After 6 months, follow-up tomographic examination will be completed for volumetric analysis.

Study Population

Patients of the Graduate Periodontology clinic requiring implant therapy will be screened and selected to participate in the study based on the following inclusion and exclusion criteria:

Inclusion Criteria

- Adults aged 22 years and older.
- Patients who understand and agree to this study.
- Adequate Oral hygiene
- One or more edentulous spaces, which are 10 weeks or longer after extractions
- Patients requiring signature from a Legally Authorized Representative (LAR) will be eligible to participate in the study

Exclusion criteria:

- Grafted extraction socket or ridge augmentation procedure utilizing xenogenic bone graft material.
- Pregnancy as checked via medical history
- Smoking of more than 5 cigarettes/day.
- History of alcoholism or drug abuse during the last 5 years.
- Uncontrolled Hypertension or diabetes.

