The lowest value of implant stability is at three weeks after implant placement and it is most pronounced in type IV bone. (Barewal et al, Int. JOMI 2003. Sep-Oct; 18 (5) 641-51) Implant Stability increases greatly between week 0 and week 6 and showed slow increase between week 6 and 6 months. (Jae-Min Kim et al, J. Adv. Prosthodont 2009. March; 1 (1) 31-36). Implant stability starts declining after first week and reach its lowest value at three week to start increasing in the fourth week. (Markovic et al, OOOOE 2011. November; 112, (5) 557-63) ISQ is obtained at 12 weeks to ensure implant stability prior to having implants restored.

Data and Safety Monitoring

Implant therapy, either with standard drilling or osseodensification, has some inherent possible complications such as post-operative discomfort, infection, pain, implant failure, swelling and bleeding. All clinical protocols currently in effect in the Graduate Periodontology clinic will be followed in order to minimize these risks. Currently, all patients, undergoing implant therapy at the Graduate Periodontology, receive antibiotics prophylactically, pain medications for management of pain and discomfort, steroids as needed to help with edema, and chlorhexidine mouthrinse to maintain the surgical sites clean as possible by reducing the bacterial load. In the event of implant failure, the implant will be removed, and the site will be grafted for future repeat of the implant therapy at the specific area.

Statistics & Computer tomography analysis

Data will be evaluated with paired T-tests. The total number of subjects enrolled in the study will be twenty and all eligible subjects will be provided with the opportunity to participate. Termination of the trial will be considered only when unexplained implant failures are observed, excluding implant failures associated with systemic conditions, infections or other well documented contributing factors in the literature.

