| In densifying mode make sure your osteotomy is 1.0 mm deeper than the actual implant final length. In extreme hard bone, utilize DAC (Densify After Cut) Protocol. Find protocol in IUD. | | | | | | | | | | | | | | | | | |
| Geometry | Major Ø | Minor Ø | Pilot | Bur 1 | Bur 2 | Bur 3 | Bur 4 | Bur 5 | Densah® Bur Block Display | Pilot | Bur 1 | Bur 2 | Bur 3 | Bur 4 | Bur 5 | Bur 6 | Densah® Bur Block Display |
| Taper | 3.0 | 2.5 | Pilot | VT1828 (2.3) | VS2228* (2.5) | — | — | — | ● ● ● ● ● ● ○ ○ ○ ○ ● ○ ○ ○ ○ ● ○ ○ ○ ○ ● ○ ○ ○ ○ | Pilot | VT1828 (2.3) | VS2228* (2.5) | — | — | — | — | ● ● ● ● ● ● ○ ○ ○ ○ ● ○ ○ ○ ○ ● ○ ○ ○ ○ ● ○ ○ ○ ○ |
| Taper | 3.5 | 3.0 | Pilot | VT1525 (2.0) | VT2535* (3.0) | — | — | — | ● ● ● ● ● ● ○ ○ ○ ○ ● ○ ○ ○ ○ ● ○ ○ ○ ○ ● ○ ○ ○ ○ | Pilot | VT1525 (2.0) | VT2535* (3.0) | — | — | — | — | ● ● ● ● ● ● ○ ○ ○ ○ ● ○ ○ ○ ○ ● ○ ○ ○ ○ ● ○ ○ ○ ○ |
| Taper | 4.3 | 3.7 | Pilot | VT1828 (2.3) | VT2838* (3.3) | — | — | — | ● ● ● ● ● ● ○ ○ ○ ○ ● ○ ○ ○ ○ ● ○ ○ ○ ○ ● ○ ○ ○ ○ | Pilot | VT1828 (2.3) | VT2535 (3.0) | VT2838 (3.3) | VS3238* (3.5) | — | — | ● ● ● ● ● ● ○ ○ ○ ○ ● ○ ○ ○ ○ ● ○ ○ ○ ○ ● ○ ○ ○ ○ |
| Taper | 5.0 | 4.2 | Pilot | VT1828 (2.3) | VT2838* (3.3) | VT3545* (4.0) | — | — | ● ● ● ● ● ● ○ ○ ○ ○ ● ○ ○ ○ ○ ● ○ ○ ○ ○ ● ○ ○ ○ ○ | Pilot | VT1828 (2.3) | VT2535 (3.0) | VT2838 (3.3) | VT3545 (4.0) | VT3848* (4.3) | — | ● ● ● ● ● ● ○ ○ ○ ○ ● ○ ○ ○ ○ ● ○ ○ ○ ○ ● ○ ○ ○ ○ |
| Taper | 5.9 | 5.0 | Pilot | VT1525 (2.0) | VT2535 (3.0) | VT3545 (4.0) | VT4555* (5.0) | — | ● ● ● ● ● ● ○ ○ ○ ○ ● ○ ○ ○ ○ ● ○ ○ ○ ○ ● ○ ○ ○ ○ | Pilot | VT1525 (2.0) | VT2535 (3.0) | VT2838 (3.3) | VT3545 (4.0) | VT3848 (4.3) | VT4555* (5.0) | ● ● ● ● ● ● ○ ○ ○ ○ ● ○ ○ ○ ○ ● ○ ○ ○ ○ ● ○ ○ ○ ○ |

*Denotes implant placement.

*Clinician experience and judgment should be used in conjunction with the Densifying Reference Guide recommendation and suggested use protocols.

MD45 REV05

Figure 2: Versah burs to be used per implant diameter for soft and hard bone.

Products to be used in this project.

| Product | Quantity | Check if Requested from Versah |
|---|----------|--------------------------------|
| Osseodensification drills - kit | 4 | X |
| Osstell ISQ | 1 | X |
| Krekler Sliding Caliper Round Gauge Dental Instrument | 1 | |
| NobelReplace® Conical implants and healing abutments | 40 | |
| Computed Tomographic scans | 20 | |

| | | |
|-----------|----------------|--|
| PTFE 4.0 | 20 | |
| Lidocaine | 1 package (50) | |

REFERENCES

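### The primary ridge width is read at 10 mm at every site, but the shortest permitted implants need a hole that ends above that level, and the plan has no rule for those readings

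*Combined protocol and SAP*

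**What the plan says.** Under Primary Outcome Measures (Study Procedures) the protocol states: "All ridge dimensions will be measured immediately after flap reflection and after final osteotomy preparation". The levels are "at crest, 5 mm and 10 mm apical from the crest", and all readings are made on the day of surgery. The before-and-after change therefore reflects drilling alone.

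Surgical technique allows a range of implants: "Implant lengths will be from 8.0 up to 13.0 mm". The only readable statement on hole depth is in the drill chart in the Attachments (Figure 2): "In densifying mode make sure your osteotomy is 1.0 mm deeper than the actual implant final length". The chart ties densifying mode to counterclockwise rotation and cutting mode to clockwise rotation. Surgical technique says: "When using Versah, counterclockwise drilling will be performed in maxilla, and in mandible clockwise drilling".

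The design is "Forty implants will be paired and placed in 20 patients", one site per technique, and the whole stated analysis is "Data will be evaluated with paired T-tests". Nothing sets a minimum implant length or hole depth for the 10 mm reading, drops that level at shallow sites, requires equal lengths within a pair, or adjusts for length.

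**The concern.** The General Information section locates the compaction effect in the walls of the drilled hole. Where the hole stops above 10 mm there is no wall at the level being measured, so the before-and-after change there should be close to zero whichever technique is used. Such pairs still enter the paired comparison at 10 mm and pull its mean toward zero.

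What is at stake is how one of the three primary levels is read. A null result at 10 mm could mean that osseodensification does not widen the ridge at that depth, or that a share of the sites was not drilled there. As written, the plan does not separate the two. The Background already cites an earlier study in these terms: "Greater changes in ridge width were noted at the crest versus 10 mm from the crest". A reader who compares levels informally could take a gradient caused partly by implant length as confirmation of that finding.

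**Working it through.** **The plan's own figure.** The sample size of 20 patients cannot be reproduced, because the protocol gives no alpha, power, effect size or SD. The calculations below are therefore illustrations under stated assumptions.

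**Step 1: geometry.** Inputs are the 10 mm level (Primary Outcome Measures), the 8.0 mm minimum length (Surgical technique) and the 1.0 mm extra depth in densifying mode (Figure 2). Two things are assumed: the implant platform sits at the crest, and where no depth rule is given the hole is as deep as the implant is long.

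| Implant length | Hole = length | 10 mm level relative to hole | Hole = length + 1.0 mm | 10 mm level relative to hole |
|---|---|---|---|---|
| 8.0 mm | 8.0 mm | 10 − 8.0 = 2.0 mm below | 9.0 mm | 10 − 9.0 = 1.0 mm below |
| 9.0 mm | 9.0 mm | 1.0 mm below | 10.0 mm | at the base |
| 10.0 mm | 10.0 mm | at the base | 11.0 mm | within, by 1.0 mm |
| 13.0 mm | 13.0 mm | within, by 3.0 mm | 14.0 mm | within, by 4.0 mm |

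Lengths under 10.0 mm fall short without the extra depth, and lengths under 9.0 mm fall short with it. An 8.0 mm implant falls short either way. The crest and 5 mm levels lie within the hole for every permitted length.

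**Step 2: effect on the mean.** Let δ be the mean difference at 10 mm in pairs that reach the level, and take it as zero in the k pairs that do not. Over all 20 pairs the expected mean is [(20 − k)·δ + k·0]/20 = δ·(20 − k)/20.

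- k = 2: 18/20 = 0.90
- k = 5: 15/20 = 0.75
- k = 10: 10/20 = 0.50

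These values of k are assumed.

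**Step 3: effect on power.** Assume a two-sided paired t-test at alpha 0.05 and a true effect in reaching pairs of d = 0.9 SD of the pair differences. All-pairs power comes from simulation. Restricted power comes from the noncentral t distribution with 20 − k pairs. Because an undrilled level should vary less, three SDs are shown for the non-reaching pairs, relative to the reaching pairs.

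| k | All pairs, equal SD | All pairs, half SD | All pairs, quarter SD | Reaching pairs only |
|---|---|---|---|---|
| 2 | 92% | 94% | 95% | 95% |
| 5 | 77% | 87% | 89% | 90% |
| 10 | 40% | 57% | 66% | 72% |

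With half the SD or less, restriction gains about 0 to 3 points at k = 2 or 5, and 6 to 15 points at k = 10. With equal SDs it gains 3, 13 and 32 points. At a smaller assumed effect of d = 0.66 (80% power if all 20 pairs reach the level) and equal SDs, all-pairs against restricted power is about 70% against 75%, 52% against 66%, and 25% against 46%.

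**The case against.** Several points on the other side stand.

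- The length mix is not stated. If no short implants are placed, k = 0 and nothing is diluted. The effect sizes have no source in the protocol either, and the cited background suggests any effect at 10 mm is smaller than at the crest.
- The largest power losses need equal SDs, which sits badly with the argument that an undrilled level barely changes. With smaller SDs the loss at k = 2 or 5 is slight.
- A fixed 10 mm level over all treated sites is a legitimate quantity to estimate, and the plan makes no formal comparison between levels.
- In pairs with unequal lengths the osseodensification site should drive most of the contrast, so the dilution formula is only approximate there.

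Two stronger readings are tempting. A reader might infer that short sites cannot show any drilling effect at 10 mm. The protocol does not state where the platform sits or that expansion stops at the base of the hole, so little or no effect is as far as one can go. A reader might also infer that depth is systematically confounded with technique, because a densifying hole is 1.0 mm deeper than a standard one. The depth of the standard hole is an assumption here, and the figure for the standard kit is not readable. The extra 1.0 mm is explicit only for densifying mode, meaning counterclockwise use, which the protocol assigns to the maxilla.

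None of this supplies the missing rule. The shrinkage of the mean does not depend on the SDs.

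**Conclusion.** The point holds in a limited form. The protocol takes a primary reading at 10 mm at every site, permits implants whose hole is expected to end 1 to 2 mm above that level, and does not say how those readings are handled. The mean 10 mm contrast is then multiplied by about (20 − k)/20. This rests on crest-level seating, negligible expansion below the hole, and a true effect at 10 mm in the sites that reach it.

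The geometry is secure given crest-level seating. The size is not known, because k is not given and may be zero. The documents do not support a claim that the trial is underpowered or that its primary result as a whole is biased: only one of three levels is touched, and the power loss ranges from negligible to large depending on assumptions. This is a cheap improvement, held with moderate confidence.

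**What to change.** In Primary Outcome Measures, state that the main 10 mm comparison uses pairs in which the planned implant length is at least 10 mm at both sites. Record planned length per site from the virtual plan before the coin toss. The protocol already places virtual planning and implant selection before surgery and assignment before flap reflection, but it does not say that planning precedes the toss, so that order should be written down. Keep crest and 5 mm on all pairs. Report the 10 mm result over all pairs as a secondary analysis, with planned length by site.

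The criterion should be implant length, not planned hole depth. If a densifying hole is 1.0 mm deeper than the implant and a standard hole is not, depth depends on assignment. Take planned lengths of 9.5 and 10 mm, if such lengths are used. With osseodensification at the 9.5 mm site, the depths are 10.5 and 10.0 mm and the pair qualifies. With standard drilling there, that depth is 9.5 mm and the pair drops out. A length rule fixed before the toss avoids this selection.

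The cost is a sentence or two and one recorded variable per site. Fewer than 20 pairs may remain at 10 mm, including the loss of some pairs whose osseodensification hole does reach the level, and the three levels then rest on different sets of pairs. The change concerns analysis only and implies nothing about which implant length to use.

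### Implants covered after the randomised drilling leave the 3- and 6-week ISQ comparisons and return at 12 weeks; paired t-tests then lose whole pairs, and any bias has an unknown direction.

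*Combined protocol and SAP*

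**What the plan says.** Study Procedures plans that "Forty implants will be paired and placed in 20 patients", one implant of each pair by osseodensification (OD) and one by standard drilling. On timing it says "Sites will be randomly assigned in comparative patients prior to flap reflection", so allocation precedes drilling.

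ISQ is a secondary outcome, read at placement (T0) and then: "Resonance frequency analysis will be measured at three weeks (T1), six weeks (T2), and twelve weeks (T3) post implant placement". The first hypothesis is that "Bone Densification protocol does not increase implant primary and secondary stability values in 0-6 wks" compared with standard drilling, which spans T0, T1 and T2.

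Four statements govern which implants are read and how they are analysed:

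- **Surgical technique:** "After T0, patients will receive a healing abutment which will be removed and repositioned for T1, T2, and T3 evaluations". No exception is made here.
- **Study Procedures, trigger:** "In any incidence of less than 1 mm buccal plate thickness has resulted after bone preparation, bone grafting will be done post implant placement", with the implant fully covered for two-stage healing. Grafted cases leave the 6-month CBCT analysis and the T1 and T2 ISQ readings.
- **Study Procedures, next sentence:** "Cases requiring two-stage healing will also be excluded from 3-week (T1) and 6-week (T2) ISQ readings", followed by their return for the T3 reading at second-stage surgery.
- **Statistics & Computer tomography analysis:** "Data will be evaluated with paired T-tests". There is no rule for a pair with one reading missing, no sensitivity analysis and no planned count of exclusions by technique.

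**The concern.** Coverage under the stated trigger is decided after bone preparation, and so after the randomised drilling. For ungrafted two-stage cases no sentence dates the decision, but the healing abutment is placed after T0, which suggests the same order. The operator necessarily knows the technique, and torque and ISQ have been taken at placement.

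A paired t-test needs both members of a pair, so one covered implant costs its partner as well. The set analysed can shrink at T1 and T2 and grow again at T3, so the course over the four visits compares different sets of patients. Two of the three readings in the hypothesis window are affected. One of them is week 3, which the protocol justifies as the low point of stability. If coverage depends on technique and on stability, the retained pairs no longer give the randomised comparison.

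**Working it through.** **Step 1. The plan's own figure.** 20 patients × 2 implants = 40, as stated. The documents give no alpha, power, effect size, standard deviation, correlation or expected two-stage rate, so the basis for 20 cannot be reproduced. All inputs below are assumptions. Tests are two-sided at 0.05.

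**Step 2. Who is covered.** Surgical technique has implants carry an abutment and be read at T1 to T3. Study Procedures has some of them covered and not read at T1 and T2. The two-stage sentence adds to the grafting sentence with the word also, and it carries no CBCT exclusion. Both features point to a second, ungrafted group with no stated criterion. On the narrower reading, where two-stage means grafted, the trigger is plate thickness after preparation. Either way the stated coverage follows drilling.

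**Step 3. Loss of pairs alone.** If a proportion q of implants is covered independently, expected pairs at T1 and T2 are 20(1 − q)².

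- q = 5%: 18.1
- q = 10%: 16.2
- q = 20%: 12.8
- q = 30%: 9.8

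Take a standardised paired effect of 0.66, which has 80% power at 20 pairs (noncentral t). Power is then 75% at 18 pairs, 70% at 16, 63% at 14, 55% at 12 and 46% at 10. No bias is needed for this loss.

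**Step 4. Coverage driven by low T0 ISQ (assumed).** Inputs:

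- ISQ standard deviation 7 and within-pair correlation 0.4
- T0-T1 correlation r of 0.7 or 0.85; the correlation of one implant at T0 with its partner at T1 is taken as 0.4r
- true OD advantage of 4 points at T0 and T1
- an implant is covered if its T0 ISQ is below a cut of 60 or 63
- mean T0 ISQ on standard drilling of 66, 70 or 74, which matters as much as the cut

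The covered share is Φ((cut − mean)/7). For example, Φ((60 − 66)/7) = 20% on standard drilling and Φ((60 − 70)/7) = 8% on OD. Pairs left are 20 × P(both T0 values at or above the cut). The T1 difference is its mean in those pairs, by simulation of 800,000 pairs.

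| Mean T0 ISQ, standard / OD | Cut | Covered, standard / OD | Pairs left | T1 difference, r = 0.7 / 0.85 |
|---|---|---|---|---|
| 66 / 70 | 60 | 20% / 8% | 15.3 | 3.41 / 3.26 |
| 66 / 70 | 63 | 33% / 16% | 12.0 | 3.14 / 2.97 |
| 70 / 74 | 60 | 8% / 2% | 18.2 | 3.69 / 3.63 |
| 70 / 74 | 63 | 16% / 6% | 16.1 | 3.50 / 3.36 |
| 74 / 78 | 60 | 2% / 0.5% | 19.5 | 3.88 / 3.84 |
| 74 / 78 | 63 | 6% / 2% | 18.6 | 3.75 / 3.69 |

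With complete data the difference has standard deviation 7√(2(1 − 0.4)) = 7.67. The standardised effect is 4/7.67 = 0.52 and power is 0.60. With coverage, power is about 0.28 to 0.41 at mean 66 and 0.43 to 0.58 at means 70 to 74 (simulation error about 0.01). Much of this is pair loss: with no bias, power would be 0.47 at 15 pairs and 0.38 at 12.

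**Step 5. Other triggers.** With no true effect and the same cut on both techniques, the estimate is 0. With random coverage of 15% of implants it is 4.0. If only low-ISQ OD implants are covered, the estimate is 4 + r(1 − 0.4) × 7 × λ. Here λ = φ(z)/(1 − Φ(z)) and z = (cut − 70)/7.

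- Cut 60: λ = 0.156, giving 4.46 (r = 0.7) to 4.56 (r = 0.85).
- Cut 63: λ = 0.288, giving 4.85 to 5.03.

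That is an overstatement.

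**Step 6. A likelihood analysis.** Under the step 4 mechanism with mean 66, a likelihood model that also uses the T0 ISQ of covered implants returns about 3.9 to 4.2 against the true 4.0.

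**The case against.** A reader might infer that the T1 and T2 contrasts are pulled toward zero because the least stable implants vanish. The documents do not support that. Nothing in them links covering an implant to low ISQ or torque. The stability thresholds they give (35 Ncm, ISQ 68) concern restoration. The one documented trigger is plate thickness, and the protocol's background says OD widens ridges, so exclusions could follow quite another pattern. Step 5 shows that the direction can reverse.

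A reader might also take it as settled that ungrafted implants are covered with no criterion. That is the better reading but not the only one: the two-stage sentence could simply continue the account of grafted cases. The need to reconcile the sections and the loss of partners stand on both readings.

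Three further points are fair. A covered implant cannot be read at T1 or T2, so the gap is missing data and not an analyst's choice. T0 and T3 are not guaranteed complete either, since failed implants are removed. And if ISQ values are high, few implants fall below the cuts and the effect is small, as the rows for means of 70 and 74 show. These limit the size of the point. They do not supply the missing rule for incomplete pairs.

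**Conclusion.** The point holds as a weakness in a secondary analysis that should be repaired. Certain from the text: some implants leave T1 and T2 and return at T3, the stated coverage follows randomised drilling, paired t-tests are the only method, and the sections disagree on whether every implant is read at T1 to T3. It follows that each covered implant removes its pair from the T1 and T2 tests and that power falls.

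Bias is possible but not shown, and its direction is unknown. If low T0 ISQ drives coverage, a true 4 points is estimated at about 3.0 to 3.4 with 12 to 15 pairs when the standard-drilling mean is 66. At means of 70 to 74 it is about 3.4 to 3.9 with 16 to 19.5 pairs. These figures rest wholly on the assumptions in step 4. The primary ridge measurements, taken on the day of surgery, are untouched.

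**What to change.** 1. Reconcile Surgical technique with Study Procedures on which implants are read at T1 and T2, and state whether two-stage healing without a graft is a separate category. The clinical decision to cover an implant stays as it is.
2. Replace the separate ISQ paired t-tests with one repeated-measures mixed model: technique, visit and technique by visit, with patient and implant-within-patient effects. Use every available reading of every implant, and take the T1 and T2 contrasts from this model. Keep the complete-pair t-tests as a sensitivity analysis.
3. Do not adjust for T0 insertion torque. It is measured after drilling and is itself an outcome of technique, so adjusting would remove part of the effect sought. If torque is used, place it in a joint or imputation model.
4. Report the number of covered implants by technique, with the reason recorded at surgery.

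The cost is SAP wording, one more recorded item and a little analysis time. The small downside is that the model assumes missingness at random given the observed ISQ. Recovery of the true difference is not shown if coverage depends on unrecorded factors, which is why the reasons should be recorded.
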